5.0 STATISTICAL METHODS PLANNED IN THE PROTOCOL AND DETERMINATION OF SAMPLE SIZE

The Sponsor will be responsible for the analysis of data from this protocol. A detailed Statistical Analysis Plan (SAP) will be written and approved prior to final database lock. The SAP will describe all planned analyses based on the statistical design of this study and the subsequent data collected. A brief overview of key statistical analyses is provided below.

5.1 STUDY DESIGN

Study design is described in Section 3.1.

5.2 TREATMENT ASSIGNMENT

This is a single-arm study where all enrolled subjects will have the ECHELON SLR utilized during the surgical procedure.

5.3 INTERVAL WINDOWS

Interval windows for the purpose of analysis in this study will not be defined outside of those already specified in the protocol for visit scheduling. The final visit occurs approximately 19 weeks after surgery, thus no interval windows need to be defined given the absence of long-term follow-up in this study. The Schedule of Events specifies a window of 14 days around the scheduling of the follow-up visits, and any information entered in the eCRFs at this visit will correspond to the associated visit. There will be no assigning of observations to time points outside of the visit to which they are recorded in the eCRFs.

5.4 PRIMARY AND SECONDARY ENDPOINTS AND ASSOCIATED HYPOTHESES

All study endpoints are described in Section 2.1 through Section 2.3. The following hypotheses will be evaluated for the primary endpoint for gastric procedures:

$$H_0: p_G \ge 14.0\%$$

 $H_1: p_G < 14.0\%$

Where p_G is the percentage of subjects experiencing at least one occurrence of bleeding, leak, or stricture through 70 days. A 95% confidence interval will be calculated for p_G based on the sample proportion of subjects experiencing the endpoint using the Normal approximation to the Binomial distribution and the upper limit of this confidence interval will be compared to 14.0% to evaluate the above hypotheses. A p-value will be determined based on the same Normal approximation methodology.

A similar methodology will be applied to the data observed in lung procedures to evaluate the following hypotheses:

H₀:
$$p_L \ge 12.0\%$$

H₁: $p_L < 12.0\%$

Where p_{\perp} is the percentage of subjects experiencing at least one occurrence of prolonged air leak or empyema through 70 days.

5.5 LEVELS OF SIGNIFICANCE

Each of the sets hypotheses above will be evaluated using a one-sided significance level of 0.025 and the overall level of significance across the study will be controlled at a value that does not exceed 0.05. Estimation of all additional endpoints will be performed using 95% confidence intervals.

5.6 ANALYSIS SETS

The summary of all performance and safety endpoints will be performed on the set of subjects in whom the ECHELON SLR is utilized during the surgical procedure. The summary of all primary and secondary endpoints will be performed by procedure group and in total.

5.7 SAMPLE SIZE JUSTIFICATION

For the gastric procedure group, a sample size of at least 99 subjects is required to have a minimum of 80% power for rejecting the null hypothesis when the expected rate of the primary endpoint is 7% based on current available literature^{1,2}. Similarly, for the lung resection group, a sample size of at least 116 subjects is required to have a minimum of 80% power for rejecting the null hypothesis when the expected rate of the primary endpoint is 6% based on current available literature³. Each calculation is determined using the Normal approximation with a one-sided significance level of 0.025 and makes the assumption of a 20% reduction in the expected rate of the primary endpoint with the ECHELON SLR. The

performance goal-based hypotheses specified in Section 5.4 are based on establishing acceptable initial performance of the ECHELON SLR by ruling out a doubling of the expected risk that has been reported in the literature for these procedures.

Accounting for an anticipated dropout rate as high as 12.5% in each procedure group leads to an initial planned sample size of 112 subjects in the gastric group and 131 subjects in the lung resection group.

Given the lack of available clinical data on the performance of the ECHELON SLR, an adaptive approach to sample size re-estimation will occur after approximately 50% of the originally planned sample size has been enrolled into each procedure group. The purpose of this interim analysis will be to estimate the rate of the primary endpoint in each group or concurrently to estimate the size of the relative reduction of this endpoint relative to the values reported in current literature. The current sample size calculation assumes an expected background rate of 7% in the gastric group, 6% in the lung resection group, and that a 20% relative reduction will be observed with the ECHELON SLR. Based on the values observed at the interim analysis time points for each group, the within-group sample sizes will be re-estimated. A sample size of 200 subjects has been set as the maximum sample size that will be pursued following the interim analysis and sample size re-estimation process in the gastric group and a maximum of 231 subjects has been set in the lung resection group.

The sample size re-estimation for each group will apply the methodology described in Lan and Trost⁴ and Wang, Keller, and Lan⁵. Following that methodology, the prespecified conditional power lower limit for futility is set at 10%, and the upper limit for maintaining the original sample size is set at 80%. Specifically, if the conditional power evaluated at the time of the interim analysis is ≤ 0.10 , the trial within that procedure group will be stopped for futility and the null hypothesis will be accepted. If the conditional power is ≥ 0.80 , then the study will continue to its originally planned completion with no sample size adjustment. If the conditional power is between 0.10 and 0.80, the sample size will be increased so as to maintain the conditional power at a target of 0.80 under the current trend of the data, up to the maximum values specified above.

As discussed in Lan and Trost, given that the lower limit of conditional power for futility is at least 0.10, the Type I error rate is controlled at the nominal level, and no adjustment to the planned significance level of 0.025 is required under this approach.

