Objective(s):	The primary objective of this study is to evaluate safety following use of ECHELON ENDOPATH Staple Line Reinforcement (ECHELON SLR) in subjects undergoing indicated gastric and lung resection procedures. The secondary objective will be to capture usability data of the device.				
Overview of Study Design:	This prospective, single-arm, multi-center study will collect clinical data in a post-market setting by procedure group (gastric and lung resection). Investigators will perform each procedure using the device in compliance with their standard surgical approach and the ECHELON SLR instructions for use (IFU).				
	Subjects will be consented and screened anytime during a period of 8 weeks prior to the date of surgery. Subjects will be considered treated when at least one ECHELON SLR has been placed during the procedure. All treated subjects will be followed post-operatively through discharge and again at 28, 70, and 135 days (± 14 days) post-surgery; therefore, from the surgery date to study exit, the duration will be approximately 19 weeks.				

Number of Subjects:

A minimum of 243 treated subjects (maximum of 431 treated subjects) will be included in the study from up to 16 sites in the United States with the following procedure targets:

- A minimum of 112 treated subjects for gastric procedures; and
- A minimum of 131 treated subjects for lung resection procedures.

Given the lack of available clinical data on the ECHELON SLR, an adaptive approach to sample size re-estimation will occur after approximately 50% of the originally planned sample size in each group has been enrolled. The purpose of this interim analysis will be to estimate the rate of the primary endpoint in each procedure group as well as to understand the size of the relative reduction in the rate of the primary endpoint in relation to published literature. Based on these observed values, the sample size will be re-estimated. Upon completion of the sample size re-estimation, the Sponsor will determine if enrollment will continue to the originally planned enrollment values above (the minimum number listed above for each procedure group), stop at the time of the interim analysis due to futility, or increase the sample size in one or both groups if the true endpoint rate or effect size differ from the original estimates.

Criteria for Inclusion:

Subjects satisfying the following criteria will be considered eligible for enrollment in this study:

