3.2 STUDY POPULATION

3.2.1 Enrollment

Subjects will be recruited from the PI's existing patient population who plan to have an elective gastric or lung resection surgical procedure. Eligible subjects will be consecutively approached for participation so as to remove the potential of subject selection bias. Subjects will be considered enrolled at the time of consent signing. Subjects will be considered treated when at least one ECHELON SLR has been placed during the procedure. Gastric procedures are limited to laparoscopic gastric resection, robotic laparoscopic gastric resection, partial gastrectomy, gastric wedge resection, subtotal gastrectomy, laparoscopic Roux-en-Y gastric bypass, and robotic laparoscopic gastric bypass. Lung resection procedures include lobectomy, segmentectomy or wedge

resection and lung volume reduction surgery, and may be VATS or open procedures. Up to 16 centers in the United States will be selected as study sites. Each participating investigator is expected to perform a minimum of five gastric or lung resection procedures using the ECHELON SLR. A minimum of 243 treated subjects (maximum of 431 treated subjects) are planned to be in the study with a minimum of 112 treated subjects for gastric procedures and a minimum of 131 treated subjects for lung resection procedures.

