3.2.4 Screening Failures

All subjects signing consent who do not have at least one ECHELON SLR placed during their procedures will be recorded as screen failures. For subjects who are determined to be screen failures, only the relevant eCRF pages (inclusion/exclusion criteria, demographics, AEs, subject completion/discontinuation) will be completed.

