3.2.5 Removal of Subjects from Study

A subject has the right to withdraw from the study at any time for any reason without prejudice to his/her future medical care by the physician or the institution. Should a subject (or subject's legally authorized guardian/representative) decide to withdraw, 1) all data collected up to the point of withdrawal will be considered for analysis; and 2) all efforts will be made to collect and report the final visit observations as thoroughly and timely as possible. Participation may be terminated prior to completing the study for any of the reasons listed below (reasons that do not fit the categories below will be documented as "other").

Adverse Event

When the subject experiences an AE and the Investigator or Medical Monitor believes it is in the best interest of the subject to discontinue participation in the study, the subject will be withdrawn from the study.

Lost to follow-up

When contact with the subject has been lost without completing a final contact assessment, and every attempt to contact the subject has failed, the subject will be considered lost to follow-up. All attempts to contact the subject requesting his/her return for the final visit must be documented.

Withdrawal of consent

Any method of contact with the subject (or subject's legally authorized guardian/representative) in which he/she state they no longer want to participate in the study specific activities constitutes withdrawal of consent for participation in the study. When possible, the reason for withdrawal of consent will be documented.

Site Termination or Study Termination

A study site or the entire study may be terminated. When this occurs, all subjects currently enrolled at the site will be withdrawn and documented as early terminations. Reasons for site or study termination may include, but are not limited to the following:

- Administrative concerns (e.g., inadequate subject enrollment, Investigator/institution non-compliance, change of business strategy, etc.);
- Safety Issues, including those due to non-compliance, or those that substantially affect the risk to benefit ratio of the study subjects at a site or for the study as a whole; or
- Regulatory Body Mandate(s).

The Investigator has the right to terminate the subject's participation at any time. Should this be necessary, procedures for termination will be provided by the Sponsor.

Death

• When possible, the cause of death will be documented.

Other (which may include)

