3.2.6 Subject Replacement in Study

Treated subjects who withdraw or are terminated early from the study will not be replaced.

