5.9.6 Handling of Missing Data

All summaries will be performed only on subjects undergoing the scheduled procedure and only observed data will be summarized. There will be no imputation of data for early terminated subjects or for missing data within the database for the primary evaluation of the hypotheses specified above. Sensitivity analyses will be detailed in the SAP that will be designed to assess the robustness of the primary study conclusions to missing data or incomplete data on early terminated subjects.

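### The planned 112 and 131 treated subjects cover losses of about 11.6% and 11.5%, not the stated 12.5%, and the sizing matches a different test from the one that decides the trial (minor)

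*Protocol*

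**What the plan says.** For the gastric group, Protocol 5.7 says that "a sample size of at least 99 subjects is required to have a minimum of 80% power for rejecting the null hypothesis". The lung figure is 116. Both rest on a Normal approximation, one-sided 0.025, and a 20% reduction from background rates of 7% and 6%. The section continues: "Accounting for an anticipated dropout rate as high as 12.5% in each procedure group leads to an initial planned sample size of 112 subjects", and 131 for lung. SAP 7 repeats these statements. Neither document gives the inflation formula or the variance used in the sizing.

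The planned totals count treated subjects. Protocol 3.2.1 sets "a minimum of 112 treated subjects for gastric procedures and a minimum of 131 treated subjects for lung resection procedures", and the Synopsis agrees ("A minimum of 112 treated subjects for gastric procedures"). Consenting subjects "who do not have at least one ECHELON SLR placed during their procedures will be recorded as screen failures" (Protocol 3.2.4). Protocol 3.2.6 adds: "Treated subjects who withdraw or are terminated early from the study will not be replaced". For the primary test, Protocol 5.9.6 says: "There will be no imputation of data for early terminated subjects or for missing data within the database". Protocol 3.2.5, however, says that "all data collected up to the point of withdrawal will be considered for analysis".

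The decision rule in Protocol 5.4 and SAP 8.4.1 compares the upper limit of a 95% Normal-approximation interval, built on the sample proportion, with 14.0% (gastric) or 12.0% (lung).

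**The concern.** Adding 12.5% to a required number does not protect that number against a 12.5% loss, because the loss is taken from the larger total. The plan therefore names a dropout level that its own totals do not cover. Subjects without the device are screen failures and are not among the 112 and 131, so the allowance can only be for loss after treatment, and those subjects are not replaced.

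The second matter is what the 80% refers to. A reader who wants to check it against the rule that decides the trial has to guess the variance, and the two natural choices give different cut-offs, power and one-sided error.

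**Working it through.** **Inputs.** Required 99 and 116; dropout 12.5%; planned 112 and 131; one-sided 0.025 (Protocol 5.5 and 5.7, SAP 5 and 7). Performance goals p0 = 0.14 and 0.12 (Protocol 5.4, SAP 8.4.1). Assumed true rates p1 = 0.07 × 0.8 = 0.056 and 0.06 × 0.8 = 0.048.

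**Step 1: reproduce 99 and 116.** Take a z-test with the null variance, rejecting when (x/n − p0)/√(p0(1 − p0)/n) < −1.96, with power from the binomial distribution. The smallest n with at least 80% power is exactly 99 and exactly 116. Closed formulas do not give these figures: 109 and 129 (null and alternative variance), 59 and 70 (sample-proportion variance), 94 and 112 (arcsine).

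**Step 2: reproduce 112 and 131.**
- 99 × 1.125 = 111.4, rounded up to 112; 116 × 1.125 = 130.5, rounded up to 131. Both match.
- Division gives 99/0.875 = 113.1 and 116/0.875 = 132.6. Both exceed the planned totals.

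**Step 3: what the planned totals cover** (assuming that early leavers leave the denominator).
- Largest loss that keeps the minimum: 112 − 99 = 13, and 13/112 = 11.6%; 131 − 116 = 15, and 15/131 = 11.5%.
- At 12.5%: 112 × 0.875 = 98, 1 short; 131 × 0.875 = 114.6, so 114 or 115, 1 to 2 short.

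**Step 4: the two tests compared** (exact binomial, fixed design, no interim). The written rule is read as x/n + 1.96 √((x/n)(1 − x/n)/n) < p0.

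| Group, evaluable n | z-test: reject at, power, error | Confidence limit: reject at, power, error |
|---|---|---|
| Gastric 98 | ≤6, 69.0%, 0.0117 | ≤8, 90.2%, 0.0572 |
| Gastric 99 | ≤7, 80.9%, 0.0254 | ≤8, 89.7%, 0.0531 |
| Gastric 107 | ≤7, 74.9%, 0.0127 | ≤9, 92.3%, 0.0567 |
| Gastric 112 | ≤8, 82.4%, 0.0189 | ≤9, 90.2%, 0.0392 |
| Lung 114 | ≤6, 69.3%, 0.0127 | ≤8, 90.2%, 0.0605 |
| Lung 115 | ≤6, 68.5%, 0.0118 | ≤8, 89.8%, 0.0568 |
| Lung 116 | ≤7, 80.6%, 0.0257 | ≤8, 89.4%, 0.0533 |
| Lung 126 | ≤7, 74.1%, 0.0123 | ≤9, 91.8%, 0.0546 |
| Lung 131 | ≤8, 82.1%, 0.0194 | ≤9, 90.0%, 0.0400 |

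For the z-test, 99 and 116 are local peaks. Its power is below 80% at 101 to 107 gastric and 117 to 126 lung subjects. The confidence limit exceeds 0.025 one-sided error at every n shown.

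**The case against.** **The gap is trivial.** It is 1 or 2 evaluable subjects per group. The 12.5% is an upper bound, and 112 and 131 are floors. All of this stands and sets the weight: the error is minor. It does not make the stated cover right.

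**There may be no shortfall.** Protocol 5.6 and SAP 6 define the analysis set as everyone in whom the device was used, and Protocol 3.2.5 keeps data up to withdrawal. If event-free early leavers stay in the denominator, nothing is lost. Against this, the primary analysis uses observed data only, and SAP 8.8 treats absent 70-day data as missing, imputing it only as a sensitivity analysis. An inflation for dropout also makes sense only if dropouts are lost to the test. The documents leave the point open, so the shortfall is conditional.

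**The power statement can be checked.** Protocol 5.7 gives alpha, sidedness, rates and method, and 99 and 116 do reproduce. That is so, but only after a variance is inferred that the plan does not state and that differs from the written decision rule. The consequence of that difference is excess one-sided error, not lost power.

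**Stronger readings to avoid.** A reader might infer from the 69% at 98 and 114 that the trial is underpowered. The documents do not support this. The figure belongs to the inferred z-test in a fixed design, and the drop is a step in the cut-off from 7 to 6 events; smooth Normal power for gastric moves only from 0.751 at 99 to 0.745 at 98. The written rule keeps 90.2% at both 98 and 114. The trial also has a sample size re-estimation. It responds to conditional power rather than to dropout, so it does not repair the allowance, but it means that fixed-design power is not the power of the whole trial. A reader might also conclude that the totals must rise to 114 and 133. In whole subjects 113 and 132 already suffice (113 − 14 = 99; 132 − 16 = 116), and no such increase secures 80% z-test power at the smaller losses in between.

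**Conclusion.** The dropout sentence is wrong as written, and the error is minor. Provided that early leavers drop out of the denominator, the planned totals protect the plan's own minimums up to 11.6% and 11.5% loss, about one percentage point less than stated. The arithmetic is certain; the denominator condition is an assumption. No loss of the trial's overall power is shown.

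The mismatch between sizing and decision rule is also real. At 99 and 116 the sizing test rejects at 7 events or fewer, with power 80.9% and 80.6% and error 0.0254 and 0.0257. The written rule rejects at 8 or fewer, with power 89.7% and 89.4% and error 0.0531 and 0.0533 against 0.025. These figures assume true rates of 5.6% and 4.8% for power, the performance goals for error, and a fixed design.

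**What to change.** (a) Keep 112 and 131. In Protocol 5.7 and SAP 7, replace the dropout statement with wording such as: *The planned 112 and 131 treated subjects retain at least 99 and 116 evaluable subjects for losses up to 11.6% (13/112) and 11.5% (15/131).*

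(b) Name one test for both sizing and decision in Protocol 5.4 and 5.7 and SAP 7 and 8.4.1, for example the null-variance z-test that the sizing already matches. State its exact fixed-design power and one-sided error at 99/116 and at 112/131. For the z-test these are 80.9%/80.6% with 0.0254/0.0257, and 82.4%/82.1% with 0.0189/0.0194. Do not claim 80% at every smaller evaluable number, since power is 74.9% at 107 gastric and 74.1% at 126 lung.

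**Cost.** No added subjects. The stated dropout cover falls by about one percentage point. If the z-test is chosen, fixed-design power is about 8 to 9 points lower than under the confidence limit (89.7% − 80.9% = 8.8 at 99; 90.2% − 82.4% = 7.8 at 112), in exchange for error close to or below 0.025.

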2.1 PRIMARY ENDPOINT

The primary endpoint for this study is the incidence of device-related AEs through the 70-day post-procedure follow-up visit. Specific device-related AEs that will be captured and counted toward the primary endpoint are listed below.

- Gastric
 - Bleeding (defined as below)
 - Occurrence of post-operative blood transfusion deemed related to bleeding at the staple line; or
 - Return to operating room before 70-day post-procedure follow-up visit due to bleeding deemed related to the staple line;
 - Leak (defined as below)
 - Occurrence of intra-operative or post-operative gastrointestinal leak related to the staple line as documented intra-operatively, by clinical exam, or radiographically;
 - Stricture (defined as below)
 - Occurrence of stricture documented radiographically or by endoscopy along the staple line;
- Lung Resection
 - Prolonged air leak deemed related to the staple line (defined as below)
 - Greater than postoperative day 7 (procedure=day 0);
 - Empyema (defined as below)
 - Purulent fluid collection in the pleural space documented radiographically, excluding chronic empyema

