3.0 INVESTIGATIONAL PLAN

3.1 OVERALL STUDY DESIGN AND PLAN - DESCRIPTION

This prospective, single-arm, multi-center study will collect clinical data in a post-market setting by procedure group (gastric and lung resection). Investigators will perform each procedure using the device in compliance with their standard surgical approach and the ECHELON SLR IFU.

Subjects will be consented and screened anytime during a period of 8 weeks prior to the date of surgery. Subjects will be considered treated when at least one ECHELON SLR has been placed during the procedure. All treated subjects will be followed post-operatively through discharge and again at 28, 70, and 135 days (± 14 days) post-surgery; therefore, from the surgery date to study exit, the duration will be approximately 19 weeks.

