3.6.4 Visit 4 - Post-procedure Follow-up Visit

After the surgery, subjects will have a follow-up visit approximately 70 days later (+/- 14 days). This visit can be either an office visit or a telephone follow-up. Data to be collected is defined in Section 3.5.

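### Does timing the interim re-estimation by enrolment, with no rule for subjects short of 70 days, call for a change to the plan?

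*Protocol*

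**What the plan says.** The trigger is in Protocol 5.7: sample size "re-estimation will occur after approximately 50% of the originally planned sample size has been enrolled into each procedure group". The synopsis, SAP 1.2 and SAP 7 repeat it. The surrounding definitions do not line up with it:

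- Protocol 3.2.1: "Subjects will be considered enrolled at the time of consent signing". Protocol 3.1: "Subjects will be consented and screened anytime during a period of 8 weeks prior to the date of surgery".
- The target is counted differently. The synopsis asks for "A minimum of 112 treated subjects for gastric procedures", and for 131 treated lung subjects.
- Protocol 3.2.4: "All subjects signing consent who do not have at least one ECHELON SLR placed during their procedures will be recorded as screen failures". Yet Protocol 5.2 states that "all enrolled subjects will have the ECHELON SLR utilized during the surgical procedure", which uses the word as if it meant treated.
- Protocol 2.1: "The primary endpoint for this study is the incidence of device-related AEs through the 70-day post-procedure follow-up visit". Section 3.6.4 allows 14 days either side of day 70.

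Conditional power under the current trend then decides the outcome for each group. At 0.10 or below the group stops, at 0.80 or above N is kept, and in between N is raised, to at most 200 (gastric) or 231 (lung). Protocol 5.9.5 lets enrolment continue meanwhile. Protocol 5.6 analyses all subjects in whom the device was used, and 5.9.6 summarises observed data without imputation. No section sets an interim cut-off, requires 70-day status or mentions pending subjects. SAP 8.6 only refers back to SAP 7.

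**The concern.** Read literally, the interim could be run when the 56th gastric consent is signed. The last subject counted could then be 56 + 84 = 140 days from a known endpoint, or 84 days if the count is of treated subjects. Two readings of the data handling would each distort the interim:

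- With all treated subjects in the denominator, pending subjects count as event-free and the rate is biased down.
- With completers only, information falls below the intended half.

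Either way the choice between stopping, keeping N and raising N would depend partly on accrual speed. A stop meant to catch a device that cannot rule out a doubling of risk would fire less often when the true rate sits at the null.

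**Working it through.** **The plan's own figures.** A one-sample z test with null variance, one-sided 0.025, with power by binomial enumeration, gives a smallest n of 99 for 14% against 0.8 × 7% = 5.6% (power 80.9%). For 12% against 0.8 × 6% = 4.8% it gives 116 (power 80.6%). Both match Protocol 5.7. Dropout: 99 × 1.125 = 111.4, so 112; 116 × 1.125 = 130.5, so 131. Half is 56 and 65.5 (66).

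**Decision table.** The documents print no conditional-power formula, so the usual current-trend form is assumed:

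z1 = (p0 − x/n1) / √(p0(1−p0)/n1), t = n1/N

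CP = Φ[(z1√t − 1.96)/√(1−t) + z1√((N−n1)/n1)]

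Gastric, n1 = 56, N = 112:

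| Events | CP | Decision |
|---|---|---|
| 3 | 0.83 | keep 112 (so do 0–2) |
| 4 | 0.57 | raise to 182 |
| 5 | 0.28 | raise to 200 |
| 6 or more | ≤ 0.088 | stop |

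**Cut at the trigger, all treated counted.** Let s be the share of eventual events already visible. At a true 14%, P(stop) = P(Bin(56, 0.14s) ≥ 6). For success, the hidden events are restored at the final test.

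| s | P(stop) at 14% | Success at 5.6% |
|---|---|---|
| 1 | 0.81 | 0.869 |
| 0.90 | 0.72 | 0.881 |
| 0.75 | 0.54 | 0.882 |
| 0.50 | 0.20 | 0.853 |

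At s = 0.95, P(stop) is 0.77. Lung (66 of 131) behaves alike. P(stop) at 12% is 0.82, then 0.73 and 0.55 at s = 0.9 and 0.75; success at 4.8% is 0.866, then 0.879 and 0.880. Type I error is 0.016 to 0.023 over these cases and the completer cases below. With the sample-proportion variance of Protocol 5.4 at both looks, gastric P(stop) at 14% is 0.68, then 0.57 and 0.37. Type I error is then 0.038 with complete data and 0.041 and 0.042 at s = 0.9 and 0.75. That level comes from the variance choice, which is a separate matter; immaturity adds under half a point.

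**Completers only.** With 28, 34 or 45 gastric completers, P(stop) at 14% is 0.57, 0.72 or 0.77 and success at 5.6% is 0.879, 0.824 or 0.848. With 33 or 40 lung completers, success at 4.8% is 0.876 or 0.818. The pattern is uneven because the rule acts on whole events. Very few completers do cost power. With 12, no event keeps 112, one raises N to 200, and two or more stop. At 5.6% these have probabilities 0.944^12 = 0.501, 12 × 0.056 × 0.944^11 = 0.357 and 0.143. The final test passes with at most 8 events of 112 or 18 of 200, so success = 0.501 × P(Bin(100, 0.056) ≤ 8) + 0.357 × P(Bin(188, 0.056) ≤ 17) = 0.501 × 0.892 + 0.357 × 0.981 = 0.796. The same enumeration with 14 completers gives 0.767. But 12/112 = 11% and 14/112 = 12.5%, far from about half.

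**How large s might be.** Accrual and event timing are not in the documents. Suppose the first 56 accrue evenly over A days, a fraction f of events occurs at or near surgery, and the rest fall evenly to day 70. Then s = f + (1 − f)(1 − 35/A).

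**What a wait would buy.** Suppose the interim waits 77 days (midpoint of 70 to 84) while enrolment runs on. A stop then happens with 56 + 56 × 77/A treated. For A = 180 at a true 14%: 0.8142 × 80.0 + 0.0366 × 112 + 0.0554 × 182 + 0.0938 × 200 = 65.1 + 4.1 + 10.1 + 18.8, about 98. Without the wait a stop happens at 56, with the lower stop probability for that s.

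| A (days) | s, f = 0.5 / f = 0 | Expected treated N, no wait (f = 0.5 / f = 0) | With wait |
|---|---|---|---|
| 90 | 0.81 / 0.61 | 99 / 122 | 118 |
| 180 | 0.90 / 0.81 | 88 / 99 | 98 |
| 365 | 0.95 / 0.90 | 83 / 88 | 88 |

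Waiting treats more subjects when half the events are early, and about the same or slightly fewer when they are spread evenly. At A = 90 a stop would come with about 104 of 112 already treated.

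**The case for a change.** The best argument for a change is that the rule turns on single events: one unseen event separates a stop from a rise to 200. The study is open-label with no data monitoring committee, and the sponsor analyses its own data, so an unwritten cut-off could be chosen after looking. The remedy costs only wording. Part of this stands. The gap is real, the trigger and the target count different things, and an interim on a dozen completers would be a poor one.

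It does not carry further, for three reasons. First, the text does not direct an immature cut. *After* sets an earliest time, and the stated purpose is to estimate a rate defined through 70 days. The observed-data rule in Protocol 5.9.6 also lets an analyst use only subjects with known status. The SAP tables that put all treated subjects in the denominator belong to a plan written for the final analysis, so they do not show how pending subjects would be counted at an interim. Second, the large losses need s of 0.75 or lower. That fits poorly with endpoints that include intra-operative leak and an air leak judged just after day 7, though the documents give no event timing to settle it. Third, below 50% information is a soft charge. The trigger is approximate and based on an N inflated for dropout. Against the evaluable 99 and 116, 56/99 = 56.6% and 66/116 = 56.9%, so up to 6 gastric or 8 lung subjects can lack status before half is lost.

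**Conclusion.** No change to the plan follows. *Enrolled* is used loosely where treated is meant, and the choice of interim cohort is a detail that analysts can settle sensibly from the stated purpose and the observed-data rule. If it were settled badly, the main effect would be fewer futility stops at the null rate: gastric 0.81 to 0.72–0.77 for s of 0.90–0.95, and to 0.54 at s = 0.75. In the all-treated reading, success at the gastric design rate moves by under 2 points. With 28 or more gastric, or 33 or more lung, completers it stays at 0.818 or higher. It drops just below 80% only for an interim on about 12 to 14 gastric completers, which would not meet the plan's own timing of about half. Type I error shifts by under half a point, and the final test uses full 70-day data in every case. Prescribing complete follow-up would trade a better-informed stop against more subjects treated before it, with no clear net gain. These sizes rest on assumed accrual, event timing and conditional-power formula, none of which the documents give.
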